2 STUDY SUMMARY AND AIMS

The purpose of this study is to determine the incidence, risk factors and adverse events consequent upon atrial fibrillation after cardiac surgery, as well as the association between prior atrial fibrillation and postoperative atrial fibrillation. The study uses information from local Cardiac Surgical Programs to describe the preoperative medical state and immediate post-operative state. Additionally, information from the post-discharge period will be provided by CHIA, by matching the two sources of information using HIPAA-waived data such as medical record number, date of birth, gender and last name. Once matched, the data are stripped of identifiers.

2.1 Study Design:

We will employ a retrospective cohort design, examining patients who underwent cardiac surgery at Cardiac Surgical Programs in Massachusetts between 1/1/2012 and 12/31/2016, with a follow-up period that extends to 12/31/2017. The study examines the risk factors and incidence of post-operative atrial fibrillation, stroke and other focal neurological events after discharge from hospital.

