2.4 Secondary Aims

The Secondary Aims of this study are to determine:

1. The frequency of, and treatments for, atrial fibrillation occurring after discharge from hospital in patients who underwent cardiac surgery during admission.
2. The frequency of stroke or other focal neurologic event occurring after discharge from hospital in patients who underwent cardiac surgery during admission
3. The incidence of all-cause and stroke-related mortality after cardiac surgery.

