3.4 Unrelated outcomes

Un-related events such as upper or lower limb fracture and xxx will be used as negative controls.

Unrelated adverse events (such as upper or lower limb fracture), which are known not to be caused by prior AF will be used as the composite negative control outcome to examine whether there is unmeasured confounders of the prior AF-postoperative AF association. An observed association between prior-AF and the negative control outcome will reflect the existence of unmeasured confounders. In such cases, these unmeasured confounders will also affect the true prior AF-postoperative AF association (45). When such unmeasured confounding effect is detected, we will provide an adjusted estimate for the hazard ratio of first postoperative AF using an indirect approach (46)

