7.1.2 Secondary Aims

Means and standard deviations will be estimated for count outcomes. We will report the two-sided p-value for statistical significance of the difference in means of count outcomes.

The frequencies of atrial fibrillation and stroke or other focal neurologic event will be modeled with Poisson regression with the length of follow-up time as the offset. Potential risk factors included in this model will be selected based on univariate test results, as well as clinical significance. Logistic regression will be used to model the incidence of all-cause and stroke-related mortality after cardiac surgery, respectively.

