7.6 Sensitivity Analyses

The negative control outcome analysis mentioned in section 3.4 will be part of the sensitivity analyses, which evaluates whether there is unmeasured confounding effect in the prior AF-postoperative AF association. A similar analysis will be performed for stroke, and all-cause mortality. Additionally, we will report E-values for the associations from these models. The E-value is defined as the minimum strength of association, that an unmeasured confounder would need to have with both the exposure and the outcome to fully explain away a specific exposure-outcome association, conditional on the measured covariates

When patient characteristics are significantly different between the prior AF group and non-prior AF group, stratified proportional hazard models with two sets of coefficients will be fitted, and the effects of risk factors will be evaluated. Consistency of the two sets of coefficients would reflect the imbalance of baseline variables is negligible, and one final model will be reported. For the analysis of recurrent data, consistency of the results from AG and PWP models will be monitored.

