12 APPENDIX: SHELL TABLES AND FIGURES

12.1 Tables

Table 1: Characteristics of the study participants.

Table 2: Comparison of characteristics of patients with post-discharge atrial fibrillation and those patients who did not have post-discharge atrial fibrillation

Table 3: Time-adjusted risk of post-discharge atrial fibrillation

Table 4: Time-adjusted risk of post-discharge stroke

Table 5: Time-adjusted risk of post-discharge mortality

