12.2 Figures

Figure 1: CONSORT diagram

Figure 2: Time course of the occurrence of post-discharge AF

Figure 3: Time course of the occurrence of post-discharge stroke stratified by occurrence of post-discharge AF

Figure 4: Time course of the occurrence of post-discharge mortality stratified by occurrence of post-discharge AF

Table 1: Characteristics of the study participants. Data are reported as number and percentage, or median and 10-90% quantiles, as appropriate

CSP = Cardiac surgical program

CHIA = Center for Health Information and Analysis

	Patient characteristic	Data source	Source variable
0	Demographics		
1	Age at surgery (years; N/%)	CSP	Calculated
2	<50		SurgDt - DOB
3	50-59		
4	60-69		
5	70-79		
6	≥80		
7	Gender (Male; N/%)	CSP	Gender
8	Race (Caucasian; N/%)	CSP	RaceCaucasian
9	Ethnicity	CSP	Ethnicity
10	Height (cm; mean/SD)	CSP	HeightCm
11	Weight (kg; mean/SD)	CSP	WeightKg
12	BMI (kg/m ² ; N/%)	CSP	Calculated
13	<20		
14	20-24.9		
15	25-29.9		
16	30-34.9		
17	≥35		
18	Payor		
19	Government	CSP	PayorGov
20	Commercial	CSP	PayorComm
21	HMO	CSP	PayorHMO
22	Prior Medical History		
23	Atrial fibrillation	CSP and CHIA	ArrhythAFib, ArrythAFibDur, ArrythAFibTy
24	Atrial flutter	CSP and CHIA	ArrhythAFlutter
25	History of arrhythmia	CSP and CHIA	
26	Heart block or sick sinus syndrome	CSP and CHIA	ArrhyVtachSicSinSyn, ArrhyTHB, ArrhyVtachHrtBlk, ArrhythSSS

27	VT/VF	CSP and CHIA	ArrhyVtach, ArrhythVV
28	Smoker past or current	CSP	TobaccoUse, CigSmoker, SmokCurr
29	COPD	CSP	ChrLungD
30	Diabetes	CSP	Diabetes, DiabCtrl
31		NIDDM	
32		IDDM	
33	Dyslipidemia	CSP	Dyslip
35	Dialysis	CSP	Dialysis
36	Hypertension	CSP	Hypertn
37	Peripheral vascular disease	CSP	PVD
38	Sleep apnea	CSP	SlpApn
39	Alcohol use	CSP	Alcohol
40	Cerebrovascular disease	CSP	CVD
41	Prior CVA	CSP	CVA, CVAWhen
42	TIA	CSP	CVDTIA
43	Carotid Stenosis	CSP	CVDCarSten
44	Prior carotid surgery	CSP	CVDPCarSurg
45			
46	Medications		
47	ACEI/ARB	CSP	MedACEI48
48	Anticoagulant or anti-platelet drug	CSP	MedACoag
49	Amiodarone	CSP	MedAmiodarone
50	Aspirin	CSP	MEDASA
51	Beta blocker	CSP	MedBeta
52	Calcium channel blocker	CSP	MedCChanTher
53	Antiarrhythmic	CSP	MedAarry
54	Coumadin	CSP	MedCoum
55			
56	Prior Cardiac Status		
57	Heart failure		PriorHF
58	Prior MI		PrevMI, MIWhen
59		Past	
60		Recent	
61	Prior CABG surgery	CSP	PrCAB

62	Prior mitral valve surgery	CSP	PrValveProc1, PrValveProc2, PrevProcMVReplace, PreProcMVRRepair

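### Mortality is modelled by logistic regression with no time horizon, although potential follow-up runs from 1 to 6 years and the planned mortality outputs are time-based

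*Combined protocol and SAP*

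**What the plan says.** Secondary Aim 3 (Section 2.4) is "The incidence of all-cause and stroke-related mortality after cardiac surgery". Neither the aim nor the endpoint list in Section 3.1 gives a time window. Section 7.1.2 supplies the method: "Logistic regression will be used to model the incidence of all-cause and stroke-related mortality after cardiac surgery, respectively". In the same paragraph the frequencies of AF and of stroke or other focal events are to be "modeled with Poisson regression with the length of follow-up time as the offset", and Section 7.1.1 uses Cox models for first AF and first neurologic event. Neither device is extended to mortality.

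Section 2.1 takes operations "between 1/1/2012 and 12/31/2016, with a follow-up period that extends to 12/31/2017".

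The shells in Section 12 include "Table 5: Time-adjusted risk of post-discharge mortality" and "Figure 4: Time course of the occurrence of post-discharge mortality stratified by occurrence of post-discharge AF". Table 1 has descriptive rows for mortality at 30 days, 1 year and 5 years, all sourced to the cardiac surgical programs (CSP). Section 1.1, however, describes program data as ending at hospital discharge and assigns the later course to CHIA.

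**The concern.** A logistic model needs an outcome that is known, over the same period, for everyone in it. Here a patient operated on in January 2012 can be observed about six times as long as one operated on in December 2016. Without a horizon, whether a patient is recorded as dead depends partly on the date of surgery. The resulting incidence and odds ratios then describe no stated period.

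The method and the outputs also do not fit together. A logistic model without a time axis yields neither a time-adjusted risk nor a time course, and no survival model for mortality is named. The time origin differs too: the aim counts from surgery, whereas Table 5 and Figure 4 count from discharge.

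How much this matters depends on how far deaths are captured, which the plan does not settle. If they are captured to 12/31/2017, the problem is real. If capture stops at discharge or at 30 days, the window is nearly fixed and logistic regression is adequate, but several planned outputs cannot be filled as labelled.

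**Working it through.** **Plan's own figure.** None is given for mortality. The only power statement (Section 4) concerns postoperative AF: (1.960 + 0.842) × √(1/4,000 + 1/46,000) = 0.046. It reproduces and is unaffected by this point.

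**Follow-up (dates from Section 2.1).** Surgery on 1/1/2012 gives 2,191 days to the close, 2,191/365.25 = 6.0 years. Surgery on 12/31/2016 gives 365 days, 1.0 year. Over the 1,827 possible surgery dates the mean is 3.5 years. Surgery dates in 2012 number 366, so under even accrual 366/1,827 = 20.0% can reach 5 years. If accrual rose or fell 1.5-fold over the period, the share is 16.8% or 23.2%. All patients can reach 30 days and 1 year.

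**Assumptions for size.** The documents give no death rate. I assume early operative mortality e of 0, 3 or 5%, then a constant hazard h of 2, 4 or 8% per year, the same for every operation year, with deaths captured to 12/31/2017. Cumulative death is F(t) = 1 − (1 − e)·exp(−h·t).

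**5-year row.** The true value is F(5). Deaths within 5 years over all patients is the mean of F(min(follow-up, 5)) across surgery dates. For e = 0.03 and h = 0.04, F(5) = 1 − 0.97 × exp(−0.20) = 0.206. The all-patient figure is 0.152, so it reads 1 − 0.152/0.206 ≈ 26% low. Percentages and odds ratios in the table use unrounded values; the three entries per cell are h = 2, 4 and 8%.

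| e | True F(5) | Deaths over all patients | Reads low by | Ever-died OR, 2012 vs 2016 operations |
|---|---|---|---|---|
| 0% | 0.095 / 0.181 / 0.330 | 0.065 / 0.126 / 0.234 | 31 / 31 / 29% | 3.8 / 4.0 / 4.3 |
| 3% | 0.122 / 0.206 / 0.350 | 0.093 / 0.152 / 0.257 | 24 / 26 / 27% | 2.4 / 3.0 / 3.7 |
| 5% | 0.140 / 0.222 / 0.363 | 0.112 / 0.170 / 0.272 | 20 / 24 / 25% | 2.1 / 2.6 / 3.4 |

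The last column shows how strongly length of follow-up enters the outcome when the hazards are identical. It is not an estimate that any aim asks for. Restricting the 5-year row to 2012 operations recovers F(5), using a fifth of the data.

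**Prior-AF odds ratio under a null effect.** With constant prevalence (8%, Section 4) it is 1.00. If prevalence is assumed to move from 6% to 10% over 2012-2016, it is 0.93-0.96 with linear drift and 0.91-0.95 with yearly steps. For 10% to 6% it is 1.04-1.08 and 1.05-1.09. With operation year in the model (linear drift) it is 0.997-1.003.

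**Death source.** Table 1 names CSP for 1- and 5-year mortality. Section 1.1 runs program data to discharge. Appendix 9 requests date and cause of death from programs without saying how far they extend. The field list in Appendix 10 is described as the minimum for the merge, so it neither shows nor excludes post-discharge deaths.

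**The case against.** The best defence is that Table 1 does name horizons, that Section 7.1 reports odds ratios for each binary outcome, and that logistic regression at 30 days and 1 year is sound. On that reading the plan lacks only a cross-reference. Part of this stands: it would be wrong to say that the plan contains no mortality horizon. But the Table 1 rows are descriptive, Section 7.1.2 does not refer to them, about four-fifths of patients cannot reach the 5-year row, and Table 5 and Figure 4 would still have no method.

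The second defence is that the main exposure, prior AF, is barely touched. That stands in full. A reader might infer from the odds ratios of 2.1 to 4.3 that the prior-AF result for mortality is badly biased. Those figures concern operation year, which no aim studies. The drift needed to move the prior-AF odds ratio is assumed, and operation year is collected, although not named as a required covariate.

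Three other stronger readings are not supported:

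- Section 7.6 says "A similar analysis will be performed for stroke, and all-cause mortality", and Section 3.4 says "we will provide an adjusted estimate for the hazard ratio of first postoperative AF using an indirect approach". One might infer that a mortality hazard ratio is promised. Section 3.4 ties the hazard ratio to first postoperative AF, so this is inference only.
- Section 7.3 excludes patients with missing outcomes. Dropping survivors not yet at 5 years while keeping deaths would make the 5-year figure 1.9-2.8 times too high under the same assumptions. The plan does not say that such patients count as missing.
- One might conclude that no source holds post-discharge deaths. The documents do not show that.

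**Conclusion.** The point holds as a defect of Secondary Aim 3 only. With high confidence on the text: the mortality model has no horizon, offset or censoring; potential follow-up is 1.0 to 6.0 years; the model cannot yield Table 5 or Figure 4; and the stated death source conflicts with Section 1.1.

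The size is conditional. If deaths are captured to 12/31/2017, the incidence and odds ratios refer to no defined period, and a 5-year percentage over all patients would read about 20-31% low under even accrual and the assumed hazards. The null prior-AF odds ratio stays at 1.00 without drift, lies at about 0.91-0.96 or 1.04-1.09 under the assumed drift, and returns to about 1.00 after adjusting for operation year. If deaths are captured only to discharge or 30 days, these distortions do not arise and the fault lies in the outputs.

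It should be fixed before analysis. The primary aims and the power statement are unaffected.

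**What to change.** 1. State the source of post-discharge deaths and the last date to which they are ascertained, and reconcile Table 1 with Section 1.1.
2. If deaths are captured beyond 30 days:
   - Replace the open-ended logistic model with Cox regression for all-cause mortality, censored at the last ascertainment date and no later than 12/31/2017. Extend the proportional-hazards check of Section 7.1.1 to it. Word that section's rule that death censors so that it does not apply to this endpoint.
   - Use surgery as time origin for Aim 3. Use discharge, among patients discharged alive, for Table 5 and Figure 4.
   - Analyse stroke-related death by cause-specific Cox regression with cumulative incidence, because other deaths preclude it.
   - Report 5-year mortality by Kaplan-Meier with numbers at risk.
   - Keep logistic regression only for 30 days and 1 year from surgery, which every patient can reach.
3. If deaths are captured only to discharge, keep logistic regression for in-hospital death, and drop Table 5, Figure 4 and the Table 1 rows that cannot be filled.
4. If deaths are captured only to 30 days from surgery, keep logistic regression at 30 days and drop the 1- and 5-year rows. Limit Table 5 and Figure 4 to discharge through day 30, or drop them.
5. As a separate defect, Figure 4 groups patients by AF that occurs after time zero, so survival before AF is credited to the AF group. Treat AF as time-dependent or use a landmark.

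Cost: SAP wording and minor extra analysis. If no source holds post-discharge death dates, the cost is a further data request or a narrower mortality aim.

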7.2 Pooling of Sites

The data will be pooled across all participating sites. In logistic and Cox proportional hazards models, site will be treated as a random effect.

7.3 Methods for Handling Missing Data

The frequency and percentage of missing values for each variable will be collected, analyzed and reported. If there are missing values for the outcome variable(s), individual patients will be excluded. Highly incomplete covariates (>33% of observations missing) will be excluded from analyses. If missing values are Missing Completely At Random (MCAR), exclusion of patients with missing observations will be considered. If missing values are Missing At Random (MAR) or not at random (MNAR), multiple imputation will be performed. Missing values, selection or exclusion of observations and variables and handling of missing values in the statistical analysis will be described carefully and sensitivity analysis will be provided (48-51)

7.4 Statistical Analytical Issues

7.4.1 Adjustments for covariates

There will be covariate adjustment in the primary analysis.

7.4.2 Multiple Comparisons

There will be no adjustment for multiple comparisons. We will report 99% confidence intervals for subgroup analyses of the primary outcome.

7.4.3 Examination of Subgroups

To determine if all subgroups experience similar treatment effects or if there are subgroups that behaved differently. We will report odds ratios with 99% confidence intervals for the primary outcome by the following subgroups, with/without prior atrial fibrillation before surgery, and with/without atrial fibrillation when discharged. We will conduct a test of homogeneity of effects across the subgroups and report a P value. Unless there is strong evidence against the null hypothesis of homogeneity of effects (i.e. $p<0.001$) the overall odds ratios will be considered as the most reliable guide to the approximate relative risks in all subgroups.

7.4.4 Correlated data, bias, confounding and interactions.

Collinearity between risk factors will be evaluated with Variance Inflation Factors (VIF) or generalized VIF. Risk factors with high VIF (>2.5) will be excluded in the models.

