2.3 Primary Aims

The Primary Aims of this study are to determine:

1. The risk factors, which includes the main risk factor preoperative atrial fibrillation, for postoperative atrial fibrillation occurring after discharge from hospital in patients who underwent cardiac surgery during admission.
2. The risk factors, which includes the main risk factor preoperative atrial fibrillation, for stroke or other focal neurologic event occurring after discharge from hospital in patients who underwent cardiac surgery during admission.

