4 ESTIMATION OF ACCESSIBLE EFFECT SIZE

This will be a retrospective cohort study. Patients will be included in the study based on the inclusion and exclusion criteria. All statistical tests will be two-sided and the statistical significance level will be set at 0.05 unless otherwise stated. Assuming 50,000 patients will be included in the analysis, among which 4000 (8%) have prior AF, we will have 80% power to detect a Cohen's effect size of 0.046 at the 0.05 significance level. If 25% of the patients who do not have prior AF have postoperative AF, a Cohen's effect size of 0.046 is corresponding to a 2% difference in the incidence of postoperative AF.

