7 STATISTICAL ANALYSES

7.1 General

Baseline and demographic characteristics will be summarized using descriptive statistics (means, standard deviations or median, interquartile ranges for continuous variables such as age and percentages for categorical variables such as race and ethnicity. When deemed appropriate, they will be compared using Chi-square test, Fisher's exact test, two-sample t test, and Wilcoxon rank-sum test between groups. For each binary outcome we will report odds ratios with 95% confidence intervals and give a two-sided p-value for statistical significance. For analysis of the pre-specified subgroups (primary outcome only) we will report relative risks with 99% confidence intervals with two-sided p-value.

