7.1.1 Primary Aims

The standard Cox proportional hazards model will be used to model time to first atrial fibrillation occurrence and time to first stroke or other focal neurologic event, after discharge from hospital,

respectively. The potential risk factors included will be selected based on their univariate association with first event status, as well as clinical significance. Hazard ratios with 95% confidence intervals will be reported with a two-sided p-value for statistical significance. The proportional hazard assumption will be evaluated using graphical tool, and by including time dependent covariate terms.

Since there might be repeated occurrences of atrial fibrillation and stroke or other focal neurologic event for each patient, we will use the Andersen-Gill (AG) model and the Prentice, Williams and Peterson (PWP) models to analyze recurrent events data. The AG model is suitable when the interest is in the overall effect on the intensity of the occurrence of a recurrent event. The PWP models allow us to evaluate the effects of risk factors for the kth event after discharge from hospital, as well as the effects of risk factors for the kth event since the time from the previous event (47). Hazard ratios with 95% confidence intervals will be reported with a two-sided p-value for statistical significance. For time-to-event data analyses, death will be considered a censoring event.

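### The 99% CI subgroup analysis is a relative risk in 7.1 and an odds ratio in 7.4.3, the primary analysis is a hazard ratio, and 7.4.3 reads the odds ratio as a relative risk

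*Combined protocol and SAP*

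**What the plan says.** All references are to the combined protocol and SAP.

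- **Section 7.1, subgroups:** "For analysis of the pre-specified subgroups (primary outcome only) we will report relative risks with 99% confidence intervals with two-sided p-value".
- **Section 7.4.3, subgroups:** "We will report odds ratios with 99% confidence intervals for the primary outcome by the following subgroups", the subgroups being prior AF (yes/no) and AF at discharge (yes/no). Unless the homogeneity test gives p<0.001, "the overall odds ratios will be considered as the most reliable guide to the approximate relative risks in all subgroups".
- **Section 7.4.2** repeats the 99% level for subgroups of the primary outcome and names no measure.
- **Section 7.1.1, primary aims:** Cox models for time to first AF and time to first stroke or other focal neurologic event. "Hazard ratios with 95% confidence intervals will be reported with a two-sided p-value for statistical significance". Also, "For time-to-event data analyses, death will be considered a censoring event".
- **Section 7.1, general rule:** "For each binary outcome we will report odds ratios with 95% confidence intervals". Section 7.1.2 uses logistic regression for mortality, and 7.2 mentions logistic and Cox models together.
- **Section 4** sets the AF incidence for the size calculation: "If 25% of the patients who do not have prior AF have postoperative AF".
- **Section 2.3** makes risk factors "for stroke or other focal neurologic event occurring after discharge from hospital" a second primary aim. No incidence is given for that endpoint.
- **Sections 6.3 and 7.4.5** treat subgroup work as secondary and post-hoc, although 7.1 calls the subgroups pre-specified.

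**The concern.** Sections 7.1 and 7.4.3 describe the same table: same outcome, same subgroups, same 99% level. An analyst following one would fill it with relative risks and an analyst following the other with odds ratios. Both would comply with the plan, and neither set of numbers would be on the scale of the primary hazard ratios. The general odds-ratio sentence in 7.1 does not settle it. The primary outcomes are analysed as times to event, no logistic or relative-risk model is specified for them, and even if they were treated as binary, 7.1 itself asks for relative risks in the subgroups.

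The closing rule of 7.4.3 adds a second problem. An odds ratio stands in for a relative risk when the event is rare, and the plan assumes that AF is not. A reader applying the rule would take moderate or large AF effects as relative risks further from 1 than they are. Finally, an odds ratio or relative risk on event status ignores the unequal follow-up and the censoring at death that the Cox model handles.

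**Working it through.** **Inputs.** 50,000 patients, 4,000 with prior AF and so 46,000 without; two-sided 0.05; 80% power; 25% AF without prior AF (all section 4). Surgery from 1/1/2012 to 12/31/2016 and follow-up to 12/31/2017 (section 2.1), so potential follow-up is about 1 to 6 years.

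**1. The plan's own figure.** h = (1.960 + 0.842) × √(1/46,000 + 1/4,000) = 0.0462, against 0.046 stated. Converting, sin²(asin√0.25 + 0.046/2) = 0.270, a difference of 2.0 points. The figure reproduces and is not at fault.

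**2. Odds ratio against relative risk for AF.** With reference risk p0 and comparison risk p1, OR = [p1/(1−p1)] / [p0/(1−p0)] and RR = p1/p0. At p0 = 0.25:

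| p1 | RR | OR | OR above RR |
|---|---|---|---|
| 0.27 | 1.08 | 1.11 | 3% |
| 0.3125 | 1.25 | 1.36 | 9% |
| 0.375 | 1.50 | 1.80 | 20% |
| 0.50 | 2.00 | 3.00 | 50% |

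The two nearly agree at the minimum detectable difference and separate quickly after that. Read backwards, an OR of 3 is an RR of 2.00.

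**3. One odds ratio, different baseline risks.** RR = OR/(1 − p0 + p0 × OR). An OR of 1.80 is an RR of 1.80/1.20 = 1.50 at 25% and 1.80/1.32 = 1.36 at 40%. The 40% is my assumption. AF risk can be expected to differ across the prior-AF and discharge-AF splits, so a common odds ratio does not give a common relative risk.

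**4. Stroke.** With an assumed baseline of 1% to 5%, an RR of 1.5 is an OR of 1.51 to 1.54. The approximation is adequate there; the conflict of measures is not affected.

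**5. Follow-up.** Suppose 25% is the risk at 3.5 years (assumed) with constant hazard: −ln(0.75)/3.5 = 0.0822 per year. For a true hazard ratio of 1.5:

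| Follow-up | Risks | OR | RR |
|---|---|---|---|
| 1 year | 0.0789 vs 0.1160 | 1.53 | 1.47 |
| 6 years | 0.3893 vs 0.5228 | 1.72 | 1.34 |
| averaged over 1–6 years | 0.2447 vs 0.3401 | 1.59 | 1.39 |

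If instead half of the 3.5-year cumulative hazard falls in the first 90 days (assumed), the OR runs from 1.57 at 1 year to 1.67 at 6 years and averages 1.61, with an RR of 1.40. Under either hazard shape, one underlying effect would be reported as about 1.4, 1.5 or 1.6 depending on which section the analyst followed.

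**The case against.** The conflict between 7.1 and 7.4.3 cannot be argued away. The case on the other side is about weight and remedy.

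- **The 25% is soft.** Section 4 gives it no time horizon and does not tie it to the post-discharge endpoint. Section 1.2 cites observed incidences of 3–25% without continuous monitoring, so 25% is the top of that range. An RR of 2 is an OR of 2.06 at 3%, 2.25 at 10% and 3.00 at 25%. This stands: the approximation argument is conditional on the plan's assumption. But 25% is the only value on which the plan itself relies.
- **The 7.4.3 sentence is mainly an interpretive rule.** It tells the reader to prefer the overall estimate to the subgroup estimates, and it does say approximate. That is fair, and the rule can be kept once it is moved to another scale.
- **A single hazard ratio also implies different relative risks.** A hazard ratio of 1.5 is an RR of 1.40 at 25% baseline and 1.34 at 40%. This is correct, so step 3 counts against reading a common odds ratio as a common relative risk; it is not a reason to prefer hazard ratios.
- **The follow-up effect is modest.** An averaged OR of 1.59 to 1.61 is 6–7% above the hazard ratio of 1.5. This also stands; follow-up is a supporting point.
- **Section 7.6 already plans hazard models by prior AF.** It does, but only if baseline characteristics differ significantly, and not for AF at discharge.
- **Subgroups are secondary and post-hoc.** That limits the consequences. It does not excuse naming two measures where the plan has already fixed the subgroups, the interval level, the homogeneity threshold and the reading of the result.

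**Conclusion.** The concern holds. The contradiction between relative risk and odds ratio is certain from the text, applies to both primary endpoints and needs no assumption. The objection to reading the odds ratio as a relative risk applies to AF and rests on the plan's 25%: overstatement of 20% at an RR of 1.5 and 50% at an RR of 2, but only 3% at the detectable difference. It would shrink with a lower incidence, and it largely falls away for stroke if that event is rare. The follow-up figures depend on the assumed hazard shapes and are secondary. Only the subgroup results are affected; the primary hazard ratios and the power statement are unchanged. It should be corrected before the subgroup tables are produced.

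**What to change.** 1. In the subgroup sentence of 7.1 and in 7.4.3, report hazard ratios with 99% confidence intervals from the Cox model of 7.1.1, for each primary endpoint. Leave the general odds-ratio sentence of 7.1 as it is, since it covers the logistic mortality analysis.
2. Test homogeneity by a subgroup-by-risk-factor interaction in that Cox model.
3. Replace the last sentence of 7.4.3 with: *Unless p<0.001, the overall hazard ratio for that risk factor is the guide for all subgroups.* State that the effect of prior AF cannot be estimated within the prior-AF subgroups, so that split concerns the other risk factors.
4. Where the conditional stratified models of 7.6 are fitted, report them on the same scale.

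Any single measure used in both sections would remove the contradiction. The hazard ratio is suggested because it is the primary measure and uses follow-up time. The cost is SAP wording only: the Cox model is already planned and no new data are needed.
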